9.5. Eyelid Sulcus, Eyelid, Eyelash, and Iris Color

For changes from baseline in eyelid pigmentation, eyelid hair growth, eyelash length, eyelash thickness, eyelash pigmentation, eyelash number, and iris color/pigmentation, frequency and percentage of subjects with No change, Increased, or Decreased will be summarized by treatment and analysis visit for study eyes and for fellow eyes. For changes from baseline in eyelid sulcus, count and percentage of changes (Yes) will be summarized by treatment and analysis visit (Month 3) for study eyes and for fellow eyes. In addition, any changes from baseline in eyelid sulcus will be listed.

9.6. Vital Signs

Resting blood pressure (systolic and diastolic) and pulse rate and their change from baseline will be summarized by treatment and analysis visit.

A listing for vital signs will be provided.

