## 8.5. Subject Withdrawal Criteria

An early termination occurs when a subject who provides written informed consent ceases participation in the study, regardless of circumstances, before the completion of the study. Subjects may be voluntarily discontinued from study medication or withdrawn from the study at any time for any reason. In addition, the Principal Investigator or Medical Monitor may discontinue the study drug administration or terminate a subject's study participation due to any of the following reasons:

- AE (e.g., not compatible with study continuation)
- Non-compliance with study drug
- Lack of efficacy (e.g., IOP exceeds 34 mmHg in either eye after randomization)
- Progressive disease
- Protocol deviation (e.g., not fulfilling eligibility criteria)
- Pregnancy
- Voluntary withdrawal by subject at any time for any reason
- Lost to follow-up (e.g., no contact is possible)
- Death
- Other

If the study drug administration is discontinued prior to Visit 5, they should be encouraged to still participate in all follow-up study visits until Visit 5 on an observational basis.

[figure not shown]
If the study drug administration is discontinued prior to Visit 5, then to the extent possible, all procedures for Early Termination will be performed on the day of early drug discontinuation as per [Table 3](#) (for adult subjects) or [Table 4](#) (for pediatric subjects). Subjects who are discontinued from the study early will not be replaced.

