### 21.3.3. Vital signs (Blood pressure/Pulse rate)

Systolic blood pressure, diastolic blood pressure, and pulse rate will be measured at Visit 1 (Screening), Visit 2 (Baseline) and Visit 5 Study Exit/Early Termination. Vital signs (resting blood pressure and pulse rate) will be collected anytime at Visit 1 (Screening), and approximately 08:00 for Visit 2 (Baseline), and Visit 5 before the morning dose.

Vital signs will be collected in a sitting position after keeping quiet for more than 5 minutes.

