3.4. Visits and Assessments

There are 5 scheduled visits for each subject. Assessments at each visit and the time/visit window for each post-baseline assessment are specified in the Assessment Schedule for Adult ([Table 1](#)). If the study drug administration is discontinued prior to Visit 5, the subject should be encouraged to still participate in follow-up study visits until Visit 5 on an observational basis. For subjects whose study participation is terminated prior to Visit 5 (Month 3), to the extent possible, all assessments scheduled for Visit 5 (Month 3) will be performed at the Exit Visit.

Table 1: Assessment Schedule for ADULT Subjects

	Washout Period		Double-Masked Treatment Period			
	Visit 1 Screening	Washout Period (up to 4 weeks) Optional Visit 1a	Visit 2 Eligibility/Baseline (Day 1)	Visit 3 Week 1 (Day 8±2)	Visit 4 Week 6 (Day 43 ±3)	Visit 5 Month 3 (Day 91±7) Exit or Early Termination ⁿ
Informed Consent(s) including the optional consent for pharmacogenomics/ genomics laboratory research study ^a	X					
Inclusion/Exclusion Criteria	X		X			
Demographics and Medical History, including prior PGA ^b	X					
Concomitant Medications/ Therapies	X	X	X	X	X	X
Dosing Compliance				X	X	X
AEs		X	X	X	X	X
Pregnancy Test ^c	X		X			X
Vital Signs (blood pressure/pulse rate) ^d	X		X (08:00)			X (08:00)
Refraction ^e	X					
BCVA ^e	X	X	X (08:00)	X (08:00)	X (08:00)	X (08:00)
Biomicroscopy ^f	X	X	X (08:00)	X (08:00)	X (08:00)	X (08:00)
IOP ^g	X	X	08:00 10:00 16:00	08:00 10:00 16:00	08:00 10:00 16:00	08:00 10:00 16:00
Pachymetry ^h	X					
Instill study medication after IOP measurement				X (08:00)	X (08:00)	X (08:00)
Iris color, eyelash, eyelid ⁱ			X (photo)			X (photo)
Gonioscopy ^j	X					
Visual Field ^k	X					
Ophthalmoscopy ^l	X (pupil dilation)		X (16:00)			X (16:00, pupil dilation)
Blood Sampling for Pharmacogenomics/genomics ^m				X		

Table 1: Assessment Schedule for ADULT Subjects (Continued)

	Washout Period		Double-Masked Treatment Period			
	Visit 1 Screening	Washout Period (up to 4 weeks) Optional Visit 1a	Visit 2 Eligibility/Baseline (Day 1)	Visit 3 Week 1 (Day 8±2)	Visit 4 Week 6 (Day 43±3)	Visit 5 Month 3 (Day 91±7) Exit or Early Termination ⁿ
Dispense Study Medication			X		X	
Collect Study Medication					X	X
Phone call to remind subject to take evening dose on the day before each visit				X	X	X

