4.1.5. Out-of-Window Measurements, Analysis Visit, and Analysis Window

Analysis visit is a timing variable to be used for analyses involving visits. For each analysis visit, an *analysis window* is set up to determine the analysis visit to which a measurement should be mapped ([Table 2](#)).

The analysis visit of a measurement will be determined based on the study day of the measurement and specified analysis windows and is not necessarily the same as the study visit at which the measurement was collected. For example, an out-of-window measurement collected at the Week 1 study visit will be mapped to the Week 6 analysis visit, if the study day of the measurement falls into the analysis window of Week 6.

Table 2: Analysis Visit and Analysis Window

Analysis Visit Name (Target Day)	Protocol Visit Window	Analysis Window	
		Ophthalmoscopy, Iris Color, Eyelash, and Eyelid	Other Parameters
Baseline (Day 1)	[1, 1]	- 1]	- 1]
Week 1 (Day 8)	[6, 10]	NA*	[2, 22]
Week 6 (Day 43)	[40, 46]	NA*	[23, 61]
Month 3 (Day 91)	[84, 98]	[2 -	[62 -

*Not collected at this visit.

If there are two or more visits that fall into the same analysis window, then the visit closest to the target assessment day will be selected for that visit window. In the case that two visits are equidistant to the target assessment day, i.e., one is before and one is after the target assessment day, the later one will be selected for that visit.

For analyses of IOP involving post-baseline visits, if there are two or more visits that fall into the same analysis window of a post-baseline visit, then the visit in which IOP are measured at all the scheduled timepoints (8:00, 10:00, and 16:00) will be selected for that analysis visit first, before applying the above rule.

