4.4.2. Other Safety Measures

[Table 4](#) lists the safety measures to be evaluated for this study.

Table 4: Safety Assessments

Safety Measures	Note
BCVA	Best-corrected visual acuity will be measured for each eye at each visit under normal room illumination using visual acuity chart (e.g., ETDRS chart) and the logMAR scoring will be recorded in the subject’s source document. Increase in logMAR scores means worsening in visual acuity.

Table 4: Safety Assessments (Continued)

Safety Measures	Note
Slit-lamp Biomicroscopy	Slit-lamp biomicroscopy examinations (severity scores for 12 parameters: lid hyperemia, lid edema, conjunctival hyperemia, conjunctival chemosis, corneal staining, corneal edema, keratic precipitate, anterior chamber cells, anterior chamber flare, anterior synechiae of iris, posterior synechiae of iris, and cataract) will be performed and graded right before the 8:00 IOP measurement at all visits except Visit 1/1a (Screening or mid washout visit). Cataract severity will be assessed for subjects with phakic lens.
Ophthalmoscopy	The ophthalmoscopy (fundus) examination will be performed for each eye at Visit 1, Visit 2, and Visit 5 Study Exit/Early Termination. Variables from ophthalmoscopy are cup-to-disc ratio, glaucomatous optic nerve severity, and assessments of vitreous, retina, macula, and choroid.
Eyelid Sulcus, Eyelid, and Iris Color	The investigator (or his/her designee) will take front view and side view photograph of each eye at Visit 2 (Baseline). The photographs must include iris, eye lids and eyelashes of each eye. The photographs taken at Visit 2 (Baseline) will be used to help the Investigator assess any changes (“No changes”, “Increased”, or “Decreased”) from baseline in eyelid, eyelashes, and iris color at each follow-up visit, and assess for DUES (“Yes”, “No”) at Visit 5 Study Exit/Early Termination.
Vital Signs	Resting blood pressure and pulse rate will be collected at Visit 1, Visit 2, and Visit 5.

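### Vital signs follow ophthalmoscopy's post-baseline schedule but not its analysis window, so exit pulse and blood pressure on Days 2 to 61 are shown under Week 1 or Week 6 and not under Month 3

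*SAP*

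**What the plan says.** SAP 9.6 specifies the vital-signs analysis in one sentence: "Resting blood pressure (systolic and diastolic) and pulse rate and their change from baseline will be summarized by treatment and analysis visit". It adds a listing. It has no exit row, no last-on-treatment row and no threshold summary, and SAP 6.2.2 rules out imputation of safety scores.

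Rows are assigned by study day, not by nominal visit. SAP 4.1.5 states: "The analysis visit of a measurement will be determined based on the study day of the measurement and specified analysis windows". Table 2 in that section has two columns of windows:

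- The column headed "Ophthalmoscopy, Iris Color, Eyelash, and Eyelid" has no Week 1 or Week 6 window, with the footnote "Not collected at this visit", and its Month 3 window opens at Day 2.
- The Other Parameters column has Week 1 on Days 2 to 22, Week 6 on Days 23 to 61 and Month 3 from Day 62.

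Vital signs are not named in the first column, so they fall in the second.

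On collection, SAP Table 4 (section 4.4.2) says: "Resting blood pressure and pulse rate will be collected at Visit 1, Visit 2, and Visit 5". Protocol 21.3.3 gives the same three visits and makes clear that the last of them includes early termination. For subjects who leave the study early, SAP 3.4 says that, where possible, "all assessments scheduled for Visit 5 (Month 3) will be performed at the Exit Visit". For subjects who stop study drug early, Protocol 8.5 says that, where possible, "all procedures for Early Termination will be performed on the day of early drug discontinuation as per" the schedule of events. The same section encourages them to attend the remaining visits through Visit 5 for observation.

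**The concern.** The reason that Table 2 gives for its special column, that the measure is not taken at Week 1 or Week 6, applies equally to pulse and blood pressure. The SAP gives no reason for treating them differently. The list of safety measures that opens SAP section 9 also omits vital signs, although they are a safety endpoint in SAP 2.2.4. An oversight is therefore plausible, though not proven.

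The comparator makes this worth correcting. The timolol package insert in Protocol Appendix E reports a slight reduction in resting heart rate in some patients (mean 2.9 beats/minute, SD 10.2) and lists bradycardia and hypotension among adverse reactions. A subject who stops early for such an effect has the most informative reading on the day drug stops, and that reading is the one most likely to be missing from the Month 3 row. SAP 9.2 and 9.4 add summaries or listings of marked change for visual acuity and ophthalmoscopy. SAP 9.6 has no equivalent, so the by-visit table is the only aggregate view of the vital-sign measurements.

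**Working it through.** The plan states no figure on this point, so there is none to reproduce. The check applies Table 2 to possible exit days. I read both Month 3 windows as open at the upper end.

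**Step 1. Schedule against window** (SAP Table 1, Table 2 and Table 4)

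| Measure | Post-baseline collection | Month 3 window |
|---|---|---|
| Ophthalmoscopy | Visit 5/exit | from Day 2 |
| Iris, eyelash, eyelid | Visit 5/exit | from Day 2 |
| Pulse, blood pressure | Visit 5/exit | from Day 62 |

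**Step 2. Where an exit reading goes**

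| Exit day | Vital signs | Ophthalmoscopy |
|---|---|---|
| 15 | Week 1 | Month 3 |
| 43 | Week 6 | Month 3 |
| 61 | Week 6 | Month 3 |
| 62 | Month 3 | Month 3 |
| 70 | Month 3 | Month 3 |

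**Step 3. Share of early-exit days affected.** The protocol window for Visit 5 opens at Day 84, so early exits fall on Days 2 to 83.

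- Possible days: 83 − 2 + 1 = 82.
- Days mapped to Week 1 or Week 6: 61 − 2 + 1 = 60.
- Days mapped to Month 3: 83 − 62 + 1 = 22.
- Share outside Month 3, if exits are evenly spread: 60/82 = 73%.

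**Step 4. Illustration in subjects.** The documents give no dropout rate. With the planned 200 per arm and an assumed early-exit rate p, the number of exit readings outside Month 3 is 200 × p × 60/82:

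- p = 5%: 7.3 per arm
- p = 10%: 14.6 per arm
- p = 15%: 22.0 per arm

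This counts exit readings placed outside Month 3. It does not count subjects absent from Month 3, because those who stay for observation can have a later reading there.

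**Step 5. Subjects who stop drug but stay.** When two visits fall in one window, SAP 4.1.5 selects the one closer to the target day, here Day 91. A reading on Days 62 to 83 is at least 91 − 83 = 8 days from target. A Visit 5 within its window (Days 84 to 98) is at most 7 days away. The later, off-drug reading is therefore always selected over the one taken when drug stopped, even where that earlier reading falls in the Month 3 window.

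**Step 6. Would moving vital signs in Table 2 be enough?** Take a stop on Day 30 and a Visit 5 on Day 91. At present the Day 30 reading appears under Week 6 and the off-drug reading under Month 3. After the move alone, both fall in one window, Day 91 is selected, and the Day 30 reading appears in no summary row. The move needs a precedence rule as well.

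**The case against.** A reader might infer that early discontinuers' readings drop out of the analysis, that Month 3 describes only subjects who tolerated treatment, or that the safety comparison is biased in a way that could change a conclusion. The documents do not support these readings:

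- SAP 9.6 summarises every analysis visit by treatment, so the exit values appear in the Week 1 and Week 6 rows with change from baseline, and again in the listing.
- Bradycardia, hypotension or fatigue reported as adverse events is tabulated under SAP 9.1, which also tabulates and lists events leading to study drug discontinuation.
- SAP section 6 excludes statistical testing of safety measures, so no formal inference depends on the Month 3 row.
- Exits from Day 62 stay in Month 3 unless a later reading displaces them, and subjects who stop drug but remain can contribute a Visit 5 value.
- The Week 1 and Week 6 rows need not consist only of early exits. Protocol 7.4.6 allows assessments as needed at unscheduled visits, and note n to the assessment schedule makes the exit procedures optional there.

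Mapping by actual study day is also a legitimate choice: it avoids labelling a Day 5 reading as Month 3.

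All of this stands, and it limits the consequence. It does not explain why measures with the same post-baseline schedule are windowed differently. Nor does it supply a row that gathers each subject's last on-treatment pulse and blood pressure.

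**Conclusion.** The mapping inconsistency is established from the SAP's own text and depends on no assumption about dropout. Its effect is small. The Month 3 pulse and blood-pressure summary under-represents early discontinuers and, for those who remain under observation, shows an off-drug value in place of the on-drug one. The Week 1 and Week 6 rows will be sparse and hard to interpret.

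The 73% is a share of possible exit days and assumes even timing over Days 2 to 83. The per-arm illustration of about 7 to 22 also rests on an assumed 5% to 15% early-exit rate and should not be read as an expected count. Efficacy analyses are not affected. This is a minor point, worth correcting because the comparator is a beta-blocker and the correction is cheap.

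**What to change.** 1. In SAP 9.6, add a row for the last on-treatment value, giving value and change from baseline by treatment for pulse and for systolic and diastolic pressure. Define on-treatment explicitly; the cut-off that SAP 4.4.1 already uses for treatment-emergent events (up to 2 days after treatment end) could be reused.
2. In SAP Table 2, either move vital signs to the column used for ophthalmoscopy, with the row labelled Month 3/Exit, or mark Week 1 and Week 6 as not collected for vital signs. In either case, state that the last on-treatment reading takes precedence over a later off-drug reading, overriding the closest-to-target rule for this measure.

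The cost is two SAP edits and one more table row, with no new data. The added row mixes short and full exposure, so a footnote should say so and the by-subject listing should be kept.

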10. ADDITIONS AND CHANGES TO THE PROTOCOL-SPECIFIED ANALYSES

10.1. Full Analysis Set Definition

The full analysis set definition has been updated to add the requirement that baseline IOP data has to be present:

The Full Analysis Set (FAS) will include all randomized subjects who received at least one dose of study medication and provided Baseline IOP data (at any timepoint) and at least one post-baseline IOP measurement (at any timepoint). Efficacy analyses will be performed using the FAS and summarized by treatment as randomized.

10.2. Key Secondary Endpoint

An additional key secondary endpoint (IOP at each scheduled timepoint [08:00, 10:00, and 16:00] at Week 1 [Visit 3], Week 6 [Visit 4], and Month 3 [Visit 5] in the study eyes with mean diurnal IOP < 25 mmHg at the Baseline Visit) was added based on analysis results of a recently completed study in Asia.

10.3. Sensitivity Analysis of the Primary and Secondary Efficacy Endpoints

Protocol Amendment 1 (Version 1.1) Section 14.5, Handling of Missing Values, specified a sensitivity analysis of the primary efficacy endpoints and the secondary binary IOP endpoints (Month 3) in which missing values would be imputed using the last-observation-carried-forward (LOCF) approach. The LOCF approach is removed from the sensitivity analyses because the PMM generalizes the MMRM to include mixed missing data mechanisms beyond the MAR assumption of the MMRM. Thus, the PMM is sufficient to evaluate the robustness of the results from the MMRM.

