### **14.5. Handling of Missing Values**

The primary analysis of continuous IOP endpoints will be performed using the MMRM analysis on observed cases. As sensitivity analyses, a last-observation-carried-forward (LOCF) approach and a Pattern Mixture Models (PMM) approach may be applied to evaluate the impact of missing data on the primary analysis results. For the binary IOP endpoints, the missing data at Month 3 will be imputed using an LOCF approach.

For medical events including AEs and medical history, completely or partially missing onset and resolution dates will be imputed in a conservative fashion. Same rules will be followed to impute the completely or partially missing start and end dates of non-study medications.

Unless specified otherwise, descriptive summaries will be based on observed cases.

More details on handling of missing data will be provided in the SAP.

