4.3. Efficacy-Related Definitions

4.3.1. Response Endpoint and Response Rate

Four IOP response endpoints ([Table 3](#)) will be evaluated at each post-Baseline visit (Week 1, Week 6, or Month 3) in this study:

Table 3: Response Endpoints

Response Endpoint	Response criteria in mean diurnal IOP
IOP 20% response	Percent reduction from Baseline $\geq 20\%$
IOP 25% response	Percent reduction from Baseline $\geq 25\%$
IOP 30% response	Percent reduction from Baseline $\geq 30\%$
IOP ≤ 18 mmHg response	Mean diurnal IOP ≤ 18 mmHg

For a response endpoint, the response rate at a post-Baseline visit is calculated as the proportion of subjects who met the response criterion at the post-baseline visit.

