6.2. Handling of Missing Data

6.2.1. Efficacy Measures

For subjects with the use of any non-study IOP-lowering therapy to lower IOP, unless otherwise specified, the IOP data collected after the non-study IOP-lowering therapy will be censored (treated as missing) in efficacy analyses.

For each IOP endpoint, no imputation is needed for the analysis on observed cases using the mixed-effects model for repeated measures (MMRM). Sensitivity analysis will be performed using a Pattern-Mixture Model (PMM) approach.

In the PMM approach, Multiple Imputation (MI) with mixed missing data mechanisms will be used to investigate the appropriateness of the missing at random (MAR) assumption for missing values resulting from censoring due to the use of IOP-lowering rescue therapy, or resulting from study discontinuation due to lack of efficacy or AE.

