8. EFFICACY ANALYSES

Unless specified otherwise, efficacy analyses will be performed on the study eye, based on the FAS, and summarized by planned treatment, irrespective of the actual treatment received.

Unless otherwise specified, for subjects who receive IOP-lowering rescue therapy, any IOP values collected after the receipt of rescue therapy will be censored (i.e., treated as missing) in the analyses.

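### SAP 10.3 treats the protocol's planned Month 3 LOCF rule for the responder endpoints as a sensitivity analysis, removes it for a reason that does not apply to them, and states no replacement

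*SAP*

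**What the plan says.** Protocol 14.5 makes two separate statements. LOCF and a pattern-mixture model (PMM) are optional sensitivity analyses of the primary results. Then, in a sentence of its own and without an option: "For the binary IOP endpoints, the missing data at Month 3 will be imputed using an LOCF approach". The protocol gives no imputation rule for these endpoints at Week 1 or Week 6.

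SAP 10.3 merges the two. It says the protocol "specified a sensitivity analysis of the primary efficacy endpoints and the secondary binary IOP endpoints (Month 3"), takes LOCF out of the sensitivity analyses, and concludes: "Thus, the PMM is sufficient to evaluate the robustness of the results from the MMRM".

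The remaining SAP text on missing efficacy data is as follows.

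- Section 6.2.1: "For each IOP endpoint, no imputation is needed for the analysis on observed cases using the mixed-effects model for repeated measures (MMRM"). It also says that "the IOP data collected after the non-study IOP-lowering therapy will be censored (treated as missing) in efficacy analyses".
- Section 8: "efficacy analyses will be performed on the study eye, based on the FAS, and summarized by planned treatment", and "any IOP values collected after the receipt of rescue therapy will be censored (i.e., treated as missing) in the analyses".
- Section 4.3.1: "the response rate at a post-Baseline visit is calculated as the proportion of subjects who met the response criterion at the post-baseline visit".
- Section 8.2 names Pearson's chi-square test for the responder endpoints and says p-values will be reported. It gives no missing-data rule.

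**The concern.** A reader of SAP 10.3 would believe that only a supporting analysis had gone. For the responder endpoints, the rule being removed is the protocol's main one.

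Under LOCF, a subject without a usable Month 3 value stayed in the denominator. Under observed cases, that subject leaves it. This includes subjects who needed rescue therapy, whose later IOP is set to missing and who are the clearest treatment failures. If rescue or dropout differs between arms, the responder difference then depends on a choice that the SAP does not state. That choice would be made in programming, possibly after unmasking.

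**Working it through.** **Does the stated reason cover these endpoints?**

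| Feature | PMM (SAP 8.1.2) | Responder endpoints (SAP 2.2.3, 8.2) |
|---|---|---|
| Endpoint tier | Primary and key secondary | Other secondary |
| Analysis | Same MMRM on each of 50 imputed datasets | Pearson chi-square, 2×2 table |
| Dichotomising step | None | Needed |

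The PMM cannot show how missing data affect a chi-square test that it does not include.

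**Which rule is left?** There are three candidates, unequally supported.

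1. Observed cases. Section 6.2.1 speaks of no imputation, and sections 6.2.1 and 8 treat post-rescue values as missing. This is the most natural reading, although the 6.2.1 sentence is tied to the MMRM.
2. All FAS subjects, missing counted as not met. This would rest on the FAS wording in section 8 and the definition in 4.3.1. Neither classifies a missing value.
3. The protocol's LOCF rule still in force, because 10.3 removes LOCF only from the sensitivity analyses. Since 10.3 names the binary endpoints, removal was probably intended.

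**Size.** The plan has no figure to reproduce. From the documents: 200 subjects per arm. Assumed: everything else. The 14% and 8% missing shares average (14 + 8)/2 = 11% and differ by 6 points. That is just past the SAP 8.1.2 trigger for the trimmed-mean analysis (above 10% overall and above 5 points). The trigger concerns drug discontinuation for lack of efficacy or AE, so it is only a reference level. Discontinued subjects may still supply IOP through continued visits (SAP 3.4) or window mapping (SAP 4.1.5).

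Let r be the true response rate, m the missing share, and q the share of missing subjects who would have responded, with the same q in both arms.

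- Observed cases: (r − q·m)/(1 − m)
- All missing as non-responders: r − q·m

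The true difference is zero in every row, so each entry is an error (DE-117 minus timolol, DE-117 having the larger m).

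| r (both arms) | m | q | Observed cases | All missing as non-responders |
|---|---|---|---|---|
| 50% | 14% / 8% | 0 | 58.1 − 54.3 = +3.8 | 50.0 − 50.0 = 0 |
| 50% | 14% / 8% | 0.25 | 54.1 − 52.2 = +1.9 | 46.5 − 48.0 = −1.5 |
| 50% | 14% / 8% | 0.5 | 50.0 − 50.0 = 0 | 43.0 − 46.0 = −3.0 |
| 50% | 5% / 3% | 0 | +1.1 | 0 |
| 50% | 5% / 3% | 0.25 | +0.5 | −0.5 |
| 50% | 5% / 3% | 0.5 | 0 | −1.0 |
| 30% | 14% / 8% | 0.5 | 26.7 − 28.3 = −1.5 | 23.0 − 26.0 = −3.0 |

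First row in full: 0.50/0.86 = 0.581 and 0.50/0.92 = 0.543. The standard error of the observed-case difference at r = 50% is √(0.25/172 + 0.25/184) = 0.053, or 5.3 points. With equal missing shares, equal response and equal q, both rules give zero error.

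**Can the choice change a p-value?** Take 14% and 8% missing and observed response near 50% and 60%.

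- Observed cases: 86/172 vs 110/184, −9.8 points, p = 0.064.
- All missing as non-responders: 86/200 vs 110/200, −12.0 points, p = 0.016.
- LOCF, if 25% of carried-forward values are responses (7 of 28 and 4 of 16): 93/200 vs 114/200, −10.5 points, p = 0.036.

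The same data fall on either side of 0.05.

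**The case against.** The best defence is that observed cases is plainly meant. Section 6.2.1 opens with all IOP endpoints, censored values are called missing, and Protocol 14.5 uses observed cases by default for descriptive summaries. On that view the defect is one unwritten sentence about nominal p-values. Much of this stands: the readings are not equally supported, and a reader who infers that the SAP is evenly split between two rules goes further than the text. But the 6.2.1 sentence is limited to the MMRM, and the protocol default to descriptive summaries, so neither settles a chi-square test. If observed cases is the intent, it also removes rescued failures from the denominator, which is a substantive choice and should be stated.

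A reader might also infer that the two rules always err in opposite directions and so bracket the truth. They do not. In the last row of the error table both errors are negative. In the model used, opposite signs need q above zero and below r.

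The remaining objection is size. The missing shares are assumed, and at 5% and 3% the gap between the rules is about 1 point against a standard error near 5. That stands as a limit on importance.

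**Conclusion.** The point holds as a defect of specification. SAP 10.3 misdescribes the protocol's rule, the reason it gives does not apply to the responder endpoints, and no replacement is written.

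The size depends on assumptions. With 14% and 8% missing, true response 50% in both arms and q between 0 and 0.5, observed cases err by 0 to +3.8 points and all-missing-as-non-responder by 0 to −3.0. With 5% and 3% missing the rules differ by about 1 point. With equal missing shares and equal response there is no bias. The direction depends on how many missing subjects would have responded, which the documents cannot tell us.

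It would be wrong to infer that the responder results must favour either arm, or that the main conclusions are in doubt. These endpoints lie outside the seven-test sequence in SAP 6.4, so the primary and key secondary tests, the Type I error control and the sample size are untouched. The change should be made, but the trial's main claim does not depend on it.

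**What to change.** Before unmasking:

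1. In SAP 10.3, say that LOCF was the planned Month 3 rule for the binary endpoints and that it is replaced, and point to the new rule.
2. In SAP 4.3.1 and 8.2, set the denominator as all FAS subjects at each visit. After the window mapping of 4.1.5, count as non-responders those whose mean diurnal IOP is censored for rescue therapy, or missing after study discontinuation for lack of efficacy or AE. Section 8.1.2 already singles out this group as the one for which MAR is in doubt. For other missing values, dichotomise mean diurnal IOP in the 50 MAR-imputed datasets already planned, and combine the response differences across datasets. The p-value then comes from the combined difference and its standard error.
3. Report observed cases as the sensitivity analysis.

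The cost is SAP wording, one derivation flag and a little programming. Absolute responder rates will be somewhat lower. For illustration, let 9% and 3% of subjects be in the non-responder group (none of whom would have responded) and 5% per arm be missing for other reasons (half of whom would have). Observed-case rates are 0.475/0.86 = 55.2% and 0.475/0.92 = 51.6%. Approximating MAR imputation by the arm's observed rate, the new rule gives 0.552 × 0.91 = 50.3% and 0.516 × 0.97 = 50.1%.

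The rule is not free of error either. If a quarter of the non-responder group would in fact have responded, the same example gives 47.9% vs 49.3%, or −1.4 points. That is why observed cases should be shown beside it.
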